Mozambique is the fourth poorest country in the world (The World Bank. World Bank Open Data. Washington) and has just 15 psychiatrists and 180 psychologists to serve its population of 29 million (Santos, Wainberg et al. 2016). Given this scarcity of human resources, the Mozambican Ministry of Health (MoH) has focused on integrating psychiatric treatment into primary care, utilizing a task-shifting approach. In 1996, the MoH began training PsyTechs to deliver psychiatric services at primary care clinics through a 30-month theoretical and practical course, and PsyTechs now practice in all 135 districts of Mozambique (Santos, Wainberg et al. 2016). However, even with the introduction of PsyTechs, there are still just 1.48 mental health specialists for every 100,000 Mozambicans (Santos, Wainberg et al. 2016). Since 2017, the MoH has begun further expanding access to adult mental health services by training nonspecialists (nurses, medical technicians, and community health workers) to screen for mental disorders and provide treatment for common mental illnesses or referrals to specialized care for serious mental

illnesses. Despite this progress toward increasing services for adults, Mozambique continues to have very little infrastructure for treatment of adolescent mental disorders. The results of this study will contribute an understanding of how to integrate mental health treatment for children and adolescents in primary care clinics of low-resource settings, and its impact on patient outcomes. It will also produce data on the challenges and facilitators to implementation of mental healthcare for adolescents in these settings. This knowledge will be applied to scale-up of services in Mozambique and may be used to inform scale-up of interventions for youth globally, helping to reduce the global mental health treatment gap.

Research Aims & Abstracts

We aim to examine patient and implementation outcomes of task-shifted depression screening and group IPT-A compared to treatment as usual in a pilot cluster-randomized trial at four PCCs. Guided by Proctor's Taxonomy of Implementation Outcomes (Proctor, Silmere et al. 2011), we will assess patient and implementation outcomes through quantitative measures and post-treatment qualitative interviews with adolescents and providers in the IPT-A and TAU study arms. We hypothesize that the IPT-A arm will have better patient and implementation and patient outcomes than TAU.

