Globally, mental disorders are the largest contributor to burden of disease in adolescents (Gore Bloem et al. 2011). However, the majority of adolescents with mental illness in low- and middle-income countries (LMICs) do not have access to treatment (Kieling, Baker-Henningham et al. 2011, Patel, Kieling et al. 2013) and contextually appropriate strategies for delivering evidence-based practices for managing mental disorders are needed to expand services to these areas. To broaden engagement in care, new settings for adolescent mental health services must be identified. Evidence-based interventions for managing adolescent mental disorders integrated within primary care have been effective in high-income countries (Asarnow, Rozenman et al. 2015) but very limited data exist on how to adapt and implement these EBP in LMIC primary care (Patel, Kieling et al. 2013, Mertens, Ward et al. 2014). We previously conducted a qualitative assessment of barriers and facilitators to implementation from the perspective of adolescents, caregivers, providers, and policymakers. We then developed our plan to implement integrated adolescent depression services by holding a series of workshops with local stakeholders—including Ministry of Health and Education staff involved in adolescent, mental health, and

primary care programming; staff from local NGOs that have experience implementing adolescent health programs in primary care; and primary care providers. Now we aim to pilot test the implementation strategy developed in these workshops. We will examine patient and implementation outcomes of depression screening and group IPT-A compared to treatment as usual in a pilot cluster-randomized trial at four primary PCCs with two PCC as the IPT-A arm and two PCC as the TAU arm.

STUDY DESIGN

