We will examine patient and implementation outcomes of depression screening and group interpersonal therapy for adolescents (IPT-A) compared to treatment as usual in a pilot cluster randomized trial at four primary care clinics (PCC). Two PCC will be randomized to routine screening and IPT-A (intervention) and the other two PCC will be randomized to treatment as usual (TAU). In the IPT-A arm, providers (nurses and/or medical technicians) at PCCs will be trained to conduct paper-based depression screening as part of routine clinical care. Two providers (nurses and/or medical technicians) per clinic will be trained to facilitate group IPT-A. In the TAU arm, primary care providers will continue referring adolescents to specialized mental health services per existing protocol (when they believe the adolescent is struggling with a mental health problem or when the adolescent/their caregiver requests a referral to mental health services). Treatment providers in the TAU arm are the Psychiatric Technicians and psychologists at primary care clinics to whom adolescents are currently referred.

Study procedures

In the treatment study arm, we are evaluating the impact of IPT-A on depression symptoms in adolescents as well as the feasibility and acceptability of its introduction in primary care clinics. Therefore, adolescents identified as having depression, via screening on the PHQ-A, will be referred to IPT-A treatment groups instead of being referred to Psychiatric Technicians and psychologists in Mental Health Services at the PCC who provide unstructured psychotherapy (TAU).

IPT-A (Treatment) Study Arm: Prior to initiation of the pilot study, we will train providers at the PCC in the IPT-A arm to screen for depression using the Patient Health Questionnaire for

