Post Treatment Data Collection: After the final treatment session (either full course of treatment or after the adolescent discontinues treatment), research assistants will conduct semi-structured exit interviews with participating adolescents and their caregivers (IPT-A arm only), which will be digitally audio-recorded, to collect feedback on acceptability and appropriateness of the depression care they received. Research assistants will also conduct exit interviews, which will be digitally-audio recorded, with PCC providers (IPT-A arm only) after the completion of the pilot trial period to collect feedback on acceptability and appropriateness of depression care they provided. Data on treatment penetration (number adolescents entering treatment/ number referred), feasibility (retention in treatment, measured as number of treatment sessions completed/number of planned treatment sessions), and sustainability (penetration and retention in the 6 months following trial end) will be collected by research assistants from clinic records (both study arms).

STATISTICAL PROCEDURES

Quantitative analysis: Power was calculated conservatively based on participation of 90 adolescents, anticipating possible loss-to-follow up of ~10% as seen in similar trials (Bolton, Bass et al. 2007, Murray, Skavenski et al. 2015). Assuming an intra-PCC correlation coefficient of 0.02-

0.10,(Hemming, Girling et al. 2011) we will have 80% power to detect a moderate 0.6 to large >1.0 effect size of continuous outcomes using a two-sided z-test with an alpha level of 0.05. All analyses between arms will be based on intention to treat. Symptom change between baseline and treatment midpoint, treatment end, and 3- month follow-up will be compared in the IPT-A versus TAU study arms through mixedmodels linear regression analysis, treating PCC as a random effect and baseline symptoms and treatment arm as fixed effects. Subsequently, patient age and gender will be introduced into the model as independent fixed effects to adjust for their potential effect on symptom change. Similar analyses will be used to compare penetration, retention, and sustainability across arms. Within each arm, I will conduct exploratory analyses of the effect of adolescent age and gender on symptom change as well as provider age, gender, and years working in PCCs on fidelity to treatment using linear regression.

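### The 80% power claim rests on a z-test that four randomised clinics cannot support, and the plan names no small-sample inference for the arm comparison

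*Combined protocol and SAP*

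**What the plan says.** The Background section, under Research Aims & Abstracts, describes a pilot cluster-randomised trial at four PCCs, "with two PCC as the IPT-A arm and two PCC as the TAU arm". It also states a directional expectation: "We hypothesize that the IPT-A arm will have better patient and implementation and patient outcomes than TAU".

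Under Statistical Procedures, Quantitative analysis, power is based on 90 adolescents, about 10% loss to follow-up and an ICC of 0.02 to 0.10. The claim is: "we will have 80% power to detect a moderate 0.6 to large >1.0 effect size of continuous outcomes using a two-sided z-test", at an alpha of 0.05.

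The same paragraph compares symptom change between arms in a linear mixed model, "treating PCC as a random effect and baseline symptoms and treatment arm as fixed effects", with age and gender added afterwards. It continues: "Similar analyses will be used to compare penetration, retention, and sustainability across arms".

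Neither this section nor any other names an estimator (ML or REML), a df method, a small-sample correction or a reference distribution for the arm effect. The only reference distribution named anywhere is the z in the power sentence.

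**The concern.** Arm is assigned to clinics, so its effect is judged against the variation between clinics within arms. With four clinics and two arms, that variation is estimated on 4 − 2 = 2 df. A z-test treats it as known. The two-sided 5% critical value is 1.96 for z and 4.30 for t on 2 df, so at this size the difference decides the result.

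Two things are at stake. The stated power may be unobtainable from any test that holds its error rate with four clinics. And because the plan leaves the test for the mixed model open, the false-positive rate and the width of the confidence interval would depend on a choice made at analysis. The plan states an expectation of superiority and says that the knowledge gained will be applied to scale-up, so the arm comparison will be read as evidence.

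**Working it through.** **Inputs from the plan.** Four PCCs, 2:2; 90 adolescents; ICC 0.02 to 0.10; two-sided alpha 0.05; power 80%; claimed detectable effect 0.6 to >1.0.

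**Assumptions.** Equal clinic sizes, m = 90/4 = 22.5 (22 in the simulations); effect sizes in total-SD units; normal outcome; no gain from baseline adjustment unless stated.

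**Standard error.** Each arm mean averages two clinic means, so the difference between arms has SE = √(ICC + (1 − ICC)/m).
- ICC 0.02: √(0.02 + 0.98/22.5) = √0.0636 = 0.252
- ICC 0.10: √(0.10 + 0.90/22.5) = √0.1400 = 0.374

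**Step 1: the plan's own z-test.** Detectable effect = (1.96 + 0.84) × SE.
- ICC 0.02: 2.80 × 0.252 = 0.71
- ICC 0.10: 2.80 × 0.374 = 1.05

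The upper end agrees with >1.0. The lower end does not agree with 0.6: power there is Φ(0.6/0.252 − 1.96) = Φ(0.42) = 66%. Other readings give:

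| Reading | ICC 0.02 | ICC 0.10 |
|---|---|---|
| 81 analysed | 0.73 | 1.06 |
| 100 analysed | 0.68 | 1.03 |
| 90, one-sided | 0.63 | 0.93 |
| 90 per arm | 0.57 | 0.97 |
| 90, baseline correlation 0.5 (assumed) | 0.61 | 0.91 |

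None gives both ends of the stated range.

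**Step 2: the same SE with 2 df.** Power comes from the noncentral t distribution with critical value 4.30 and noncentrality effect/SE. The natural pairing of the plan's ranges is 0.6 with ICC 0.02 and about 1.0 with ICC 0.10.
- 0.6 SD, ICC 0.02: noncentrality 0.6/0.252 = 2.38, power 28% (z-test 66%)
- 1.0 SD, ICC 0.10: noncentrality 1.0/0.374 = 2.67, power 33% (z-test 76%)

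Power of 80% needs a noncentrality of 5.65.
- ICC 0.02: 5.65 × 0.252 = 1.43 SD
- ICC 0.10: 5.65 × 0.374 = 2.12 SD

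The plan gives no baseline correlation r. Adjustment multiplies these by √(1 − r²). With r = 0.5 assumed, they become 1.43 × 0.866 = 1.23 SD and 2.12 × 0.866 = 1.83 SD.

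As m grows without limit, SE tends to √ICC, so the detectable effect cannot fall below 5.65 × √0.02 = 0.80 SD or 5.65 × √0.10 = 1.79 SD. The limit is the number of clinics.

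**Step 3: what the open choice of test does.** Simulation of a balanced random-intercept model, 22 per clinic, 1,000,000 trials per setting. Type I error at nominal 5%:

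| Method | ICC 0.02 | ICC 0.05 | ICC 0.10 |
|---|---|---|---|
| Clinic-level t, 2 df | 5.0% | 5.0% | 5.0% |
| REML, Satterthwaite df | 5.0% | 6.6% | 7.3% |
| REML, residual-df t | 6.6% | 9.8% | 13.1% |
| REML, Wald z | 6.9% | 10.2% | 13.5% |
| ML, Wald z | 9.5% | 14.7% | 20.2% |

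The Satterthwaite error rises above 5% because its df revert to the residual value when the clinic variance is estimated as zero, which happens in 50%, 37% and 25% of trials at the three ICCs. Its power is 39% at 0.6 SD (ICC 0.02) and 35% at 1.0 SD (ICC 0.10), so it does not restore 80% either.

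**The case against.** **It is a pilot.** The plan says so repeatedly, and implementation outcomes and interviews sit beside the symptom comparison. That limits the consequence and stands as a reason not to treat this as fatal. It does not make the stated power correct.

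**Baseline adjustment will help.** It will, and the unadjusted 1.4 to 2.1 SD should always carry that condition. But even with an assumed correlation of 0.7, 2-df power at 0.6 SD is about 45% at ICC 0.02.

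**The plan names no invalid test.** This is right. A reader might infer from the power sentence that the mixed model will be tested by Wald z, and so that the trial's false-positive rate is 14% or even 20%. The documents do not support that: z is named for power only, and neither ML nor a Wald test is mentioned. What is documented is an unspecified choice.

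**The range must be read as a range.** A reader might also set 16% power (0.6 SD at ICC 0.10) against the 80% claim. The plan most naturally claims more than 1.0 SD, not 0.6, at ICC 0.10, so the fair figures are 28% and 33%.

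**An undisclosed baseline correlation may explain 0.6.** A correlation of about 0.53 gives 0.6 at ICC 0.02, but it lowers the upper end to about 0.89, contrary to >1.0.

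**Conclusion.** The concern holds. With two clinics per arm, a test that respects 2 df has roughly a third of the claimed power or somewhat more: 28/80 = 0.35 at the lower end and 33/80 = 0.41 at the upper. Separately, the lower end of 0.6 does not follow from the plan's own z-test. Both conclusions hold whether 81, 90 or 100 adolescents are analysed: the 2-df detectable effect is then 1.48 to 2.15, 1.43 to 2.12 or 1.38 to 2.09 SD over the ICC range.

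The type I error part is conditional. If Wald z were used with REML, the error would be about 7% (ICC 0.02) to 14% (ICC 0.10), and higher with ML. The plan commits to neither.

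The exact sizes rest on equal clinic sizes, total-SD units and an unknown baseline correlation. The penetration, retention and sustainability comparisons share the 2-df structure, but the plan gives no expected values or ICCs for them. For these outcomes the point is one of principle, not a demonstrated error. The plan should be corrected, but the pilot can go ahead with its present design.

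**What to change.** 1. **Restate the power.** For example: with two PCCs per arm and about 22 adolescents per PCC, a two-sided 5% PCC-level t-test on 2 df has 80% power for about 1.4 SD (ICC 0.02) to 2.1 SD (ICC 0.10) before baseline adjustment. State any baseline correlation assumed.

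2. **Prespecify the inference.** Either of these is workable:
   - At each time point, regress symptom change on baseline symptoms (then also age and gender) with PCC indicators, and compare the four adjusted PCC means between arms by a t-test on 2 df. Type I error is 5%.
   - Keep the planned mixed model, fitted by REML with Satterthwaite df. This has more power at 0.6 SD (39% against 28% at ICC 0.02), with type I error of about 5 to 7%, or about 8% with unequal clinic sizes.

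   Do not use Wald z, or residual df throughout. Nor should 2 df simply be imposed on the REML test: in simulation its type I error falls below 1% and its power at 0.6 SD is only 7 to 9%.

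3. **Report the estimate with its 95% CI as the main result** of the arm comparison, with any p-value secondary. Apply the same clinic-level principle to penetration, retention and sustainability.

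**Cost.** No change to design or data collection, and little programming. The median 95% CI half-width is about 0.9 SD (ICC 0.02) to 1.35 SD (ICC 0.10) with the 2-df t-test, against 0.45 to 0.61 SD with Wald z, which looks more precise only because it ignores uncertainty in the clinic variance. The stated detectable effect becomes less favourable, and the arm comparison becomes mainly an estimate for planning a larger trial.

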Adolescents (PHQ-A). Training will include didactics and role-plays to practice administration of the PHQ-A with corrective feedback and evaluations. Two providers per PCC will be selected to be trained on delivery of group IPT-A. Training will occur via an apprenticeship model which includes trainers (i.e., non-local experts in the mental health intervention), supervisors (i.e., local individuals chosen for an advanced role), and counselors (i.e., local individuals who provide the interventions). A group IPT-A training expert will train two psychologists from the MoH. Following this, the MoH psychologists will train the two staff members at the IPT-A arm PCC to facilitate group IPT-A. The MoH psychologists will supervise PCC providers for an additional 3 months to achieve competency prior to pilot trial initiation.

Every adolescent who attends PCCs will be screened for depression as part of their routine clinical care. Providers will use the PHQ-A for screening. Using a script, trained research assistants will introduce the study to adolescents who screen positive for depression and their caregivers. If interested, research assistants will collect patient demographic data (age in years, gender) on a questionnaire to verify eligibility.

Group IPT-A begins with one individual session, followed by ten group sessions, and ends with one individual session. As part of each Group IPT-A session, providers will collect data from adolescents on depression symptoms using the PHQ-A at treatment initiation, 6 weeks after treatment initiation (treatment midpoint), 12 weeks after treatment initiation (end of treatment), and 24 weeks after treatment initiation (3-month follow-up). The Project Coordinator will call adolescents who do not enter or who discontinue treatment to arrange data collection at these time points. For adolescents who do not enter treatment, the first scheduled session will be considered the “treatment initiation” timepoint.

Data on treatment fidelity will be collected via the Group IPT-A Fidelity Checklist, completed by the local IPT-A trainers at 10 randomly-selected sessions for each provider. On the Fidelity Checklist, providers are scored for low (1), moderate (2), or high (3) adherence to each essential element of treatment, and fidelity is measured by the total score.

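### IPT-A is given in therapy groups, but the model and power statement count only clinic clustering: the arm-effect standard error is often too small under a z reference, and the stated 0.6 is too favourable even before groups are counted

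*Combined protocol and SAP*

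**What the plan says.** Under Study procedures, IPT-A (Treatment) Study Arm, the combined protocol and SAP describes the format: "Group IPT-A begins with one individual session, followed by ten group sessions, and ends with one individual session". Two providers at each IPT-A clinic are trained to run the groups. Under Study Design, the comparator is referral to "Psychiatric Technicians and psychologists in Mental Health Services at the PCC who provide unstructured psychotherapy (TAU"); no group format is described for it. Clinics are randomised, two to each arm.

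Under Statistical Procedures, Quantitative analysis, symptom change is compared in a linear mixed model "treating PCC as a random effect and baseline symptoms and treatment arm as fixed effects". The power basis is given as: "Power was calculated conservatively based on participation of 90 adolescents", then "anticipating possible loss-to-follow up of ~10% as seen in similar trials", then "Assuming an intra-PCC correlation coefficient of 0.02" up to 0.10, and finally "we will have 80% power to detect a moderate 0.6 to large >1.0 effect size of continuous outcomes using a two-sided z-test" at alpha 0.05.

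The document gives no group size, number of groups, group ICC, group term or group identifier. The z-test is named for the power calculation only; the reference distribution for the mixed-model test is not stated.

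**The concern.** Adolescents who share ten sessions and the same facilitators are likely to have correlated PHQ-A outcomes. As described, this grouping exists in one arm only, so the design is partially nested: adolescents within groups within clinics under IPT-A, and adolescents within clinics under TAU. A model with a single PCC variance does not represent that structure, and a power statement with a single intra-PCC ICC may leave part of the variance out.

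Three things are at stake: the error rate of the arm comparison, the credibility of the stated detectable effect, and the loss of a planning quantity. This pilot of a group therapy is meant to inform scale-up. Group-to-group variance is something a larger trial would need, and it may not be recoverable if group membership is not recorded.

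**Working it through.** **Inputs from the plan.** N = 90, four clinics, two per arm, PCC ICC 0.02 to 0.10, two-sided alpha 0.05, power 80%, z-test. An equal split is assumed: n = 45 per arm and m = 22.5 per clinic.

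**Assumed, because the documents give no values.** Group size k = 6-12 and group ICC 0.05-0.15, in the IPT-A arm only and additional to the PCC ICC.

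**Formulas (SD = 1).** DE_TAU = 1 + (m - 1) × ICC_PCC. DE_IPT = DE_TAU + (k - 1) × ICC_group. SE = √[(DE_IPT + DE_TAU)/45]. Detectable effect = (1.960 + 0.842) × SE.

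**Step 1: the plan's own figure, no groups.**
- ICC 0.02: DE = 1 + 21.5 × 0.02 = 1.43; SE = √(2.86/45) = 0.252; detectable effect 0.706.
- ICC 0.10: DE = 1 + 21.5 × 0.10 = 3.15; SE = √(6.30/45) = 0.374; detectable effect 1.048.

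The upper end (above 1.0) reproduces. The lower end does not. Power at 0.6 with ICC 0.02 is Φ(0.6/0.252 - 1.960) = Φ(0.42) = 66%. With no clustering at all, the detectable effect is 2.80 × √(2/45) = 0.59, which is close to 0.6.

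The variants tried do not give both ends together (ICC 0.02 / 0.10):
- N = 81: 0.73 / 1.07
- N = 100: 0.68 / 1.03
- N = 90 with baseline R² of 0.25: 0.61 / 0.91

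**Step 2: add groups.** For example, with k = 8, group ICC 0.10 and PCC ICC 0.02: DE_IPT = 1.43 + 7 × 0.10 = 2.13; SE = √(3.56/45) = 0.281; detectable effect 0.788.

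| Groups | PCC ICC 0.02 | PCC ICC 0.10 |
|---|---|---|
| None | 0.706 | 1.048 |
| Size 6, ICC 0.05 | 0.737 | 1.069 |
| Size 8, ICC 0.05 | 0.748 | 1.077 |
| Size 8, ICC 0.10 | 0.788 | 1.105 |
| Size 12, ICC 0.15 | 0.887 | 1.178 |

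With groups of 8 and group ICC 0.05-0.10, power at 0.6 falls from 66% to 61-57% (PCC ICC 0.02).

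**Step 3: error rate of the planned model.** Trials were simulated with no arm effect: two clinics per arm, 24 per clinic, groups in IPT-A only, no baseline covariate. Nominal two-sided level 5%.

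| Analysis and true structure | PCC ICC 0.02 | PCC ICC 0.10 |
|---|---|---|
| PCC-only REML, z; no groups | 7.1% | 13.9% |
| PCC-only REML, z; three groups of 8, ICC 0.05 | 8.1% | 14.2% |
| PCC-only REML, z; three groups of 8, ICC 0.10 | 9.2% | 14.4% |
| PCC-only REML, z; two groups of 12, ICC 0.10 | 10.2% | 14.8% |
| PCC plus group effect, z; three groups of 8, ICC 0.05-0.10 | about 7% | 12-14% |
| Clinic-means t-test, 2 df | about 5% | about 5% |

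At group ICC 0.15 and PCC ICC 0.02, the PCC-only z-test gives about 10% with groups of 8 and 11-12% with groups of 12. At PCC ICC 0.10 it gives about 15%.

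**Step 4: where the excess comes from.** Take PCC ICC 0.02, group ICC 0.10 and groups of 8. The true SD of the arm difference is 0.275. The SE from clinic means is also 0.275, and the root mean squared REML SE is 0.291, so on average the squared SE is not too small. But the PCC variance is estimated at zero in 41% of trials. In those trials the mean SE is 0.20 and type I error is about 15%.

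**Step 5: what 2 df implies for power.** With the same PCC ICCs and no groups, a 2-df t-test has 80% power at about 1.4 (ICC 0.02) to 2.1 (ICC 0.10).

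**The case against.** The best defence is that the clinic is the randomised unit and the groups appear to sit within clinics. Group variance then enters the clinic means, and a clinic-level analysis accounts for it without naming it. Steps 3 and 4 bear this out: the clinic-means test holds its level. With two equal-sized clinics per arm, sharing one PCC variance across arms also does little harm to the SE of the difference. This stands, and it limits the point to z or Wald inference, a reference the plan does not state for its model.

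Second, the intra-PCC correlation could be read as total within-clinic correlation, groups included. Averaged over arms, groups add ½ × ICC_group × (k - 1)/(m - 1). From a PCC ICC of 0.02 this gives 0.02 + ½ × 0.05 × 5/21.5 = 0.026 up to 0.02 + ½ × 0.15 × 11/21.5 = 0.058, inside the plan's range. This also stands as a possible reading, but the plan does not say which is meant. It does not rescue 0.6, which fails with no group term at all.

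Third, every group input is assumed. One-arm grouping is inferred from silence: the TAU psychotherapy is not stated to be individual, and clustering by therapist in TAU is not quantified here either. That is a fair reason for moderate confidence.

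Fourth, a group term alone does not cure the error rate. At PCC ICC 0.10 it leaves 12-14%. This stands and shapes the fix.

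**Conclusion.** The omission is real: neither the model nor the power statement names therapy-group correlation, and no group identifier is planned. Its effect on the test is conditional. If a z or Wald reference is used, assumed groups of 8-12 with group ICC 0.05-0.15 raise type I error from about 7% to 8-12% at PCC ICC 0.02. At 0.10 they add only roughly one point to about 14%, and the four clinics are the main problem.

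The stated detectable effect is too favourable at its lower end: 0.71 rather than 0.6 before groups. If group correlation is additional to the intra-PCC ICC (groups of 6-12, ICC 0.05-0.15), it is 0.74-0.89 at PCC ICC 0.02, and 1.05 becomes 1.07-1.18 at 0.10.

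A reader might infer that leaving out the groups always understates the IPT-A arm's error, or that a group term would put it right. The documents do not support either. Randomisation is by clinic, so the PCC effect can carry group variance; no z reference is specified for the model; and the group inputs needed to fix a size are absent. Confidence is moderate for that reason.

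**What to change.** 1. Record a therapy-group identifier for every IPT-A adolescent, and state the planned group size and number of groups. Code adolescents who never enter a group as singletons and keep them in the intention-to-treat analysis.
2. Base the arm comparison on clinic-level, small-sample inference with about 2 df, for example a t-test on clinic means. Fit a random effect for therapy group, in the IPT-A arm only, as a supporting or sensitivity model. Report the estimated group variance as a pilot output, labelled imprecise.
3. Restate the detectable effect: correct the 0.6, say whether the ICC includes group correlation, show results over a range of assumed group ICCs (for example 0.05-0.15), and match the calculation to the test that will be used.

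The cost is one data field, one extra model and a rewritten power paragraph, with no extra patients or staff. The downsides are a less favourable stated figure, markedly so on 2 df, and a group variance estimated from only a few groups per clinic.

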TAU Study Arm: Following usual procedures, providers at the TAU arm PCC will refer adolescents who request mental health care or are suspected of mental illness to Psychiatric Technicians or psychologists at the primary care clinic. Trained research assistants will then inform these adolescents and their caregivers about the proposed study. If interested, research assistants

will administer the brief demographic questionnaire and the PHQ-A to determine eligibility. For eligible adolescents, For eligible adolescents, research assistants will conduct informed consent and assent procedures. Adolescents will be referred to treatment by mental health specialists at the PCC, per existing protocol. Research assistants will visit the PCC at the patients' treatment appointment times to collect data on depression symptoms and functioning. Similar to protocol for the IPT-A arm, data will be collected using the PHQ-A at treatment initiation, 6 weeks after treatment initiation, 12 weeks after treatment initiation, and 24 weeks after treatment initiation. While the treatment timeline in TAU will not necessarily be aligned with IPT-A (e.g. 12 weeks may not be the end of treatment that is provided), we will use these timepoints for both IPT-A and TAU adolescents to measure symptom improvement over time consistently across study arms. The Project Coordinator will call adolescents who do not enter or who discontinue treatment to arrange data collection at these time points. For adolescents who do not enter treatment, the first scheduled session will be considered the "treatment initiation" timepoint.

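### The symptom model leaves baseline undefined, uses one of two pre-treatment PHQ-A scores and names no main model; the cost is a little precision and, if the arms' source populations differ, some partly reducible bias

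*Combined protocol and SAP*

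**What the plan says.** Study Design, Study procedures, gives each adolescent two PHQ-A scores before or at the start of treatment.

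- **Entry score, IPT-A arm:** all attenders are screened, and "Providers will use the PHQ-A for screening". A positive screen leads to the study invitation.
- **Entry score, TAU arm:** adolescents who ask for care or are suspected of a mental health problem are referred. Research assistants then "will administer the brief demographic questionnaire and the PHQ-A to determine eligibility".
- **Treatment-initiation score, both arms:** taken by providers in IPT-A and by research assistants in TAU, who also take the later scores in their arm. For adolescents who never start treatment, the first scheduled session stands in.

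Statistical Procedures, Quantitative analysis, has one symptom term: the model is fitted "treating PCC as a random effect and baseline symptoms and treatment arm as fixed effects". The next sentence reads "Subsequently, patient age and gender will be introduced into the model as independent fixed effects to adjust for their potential effect on symptom change". The schedule suggests that baseline means treatment initiation, but the text never says so. It does not say which of the two models is the main one, or whether the IPT-A screening score is kept as study data.

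**The concern.** Whichever PHQ-A is called baseline, the other goes unused. Two error-prone measures of the same level predict follow-up better than one and under-adjust less. With only four clinics, patient-level covariates are a cheap source of precision, because they use none of the between-clinic degrees of freedom.

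The arms also recruit differently: screened attenders in IPT-A, requested or suspected cases in TAU. If the two source populations differ in severity, adolescents regress towards different means, and adjusting for one noisy score leaves part of that difference in the arm effect. The present wording even allows the entry score to be the single baseline, which is the worst of the three choices below. With no main model named, the choice between the estimates with and without age and gender could be made after the results are seen.

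**Working it through.** **Inputs from the plan.** "Power was calculated conservatively based on participation of 90 adolescents", so 45 per arm and 22.5 per clinic if equal; "four primary PCCs with two PCC as the IPT-A arm and two PCC as the TAU arm"; ICC 0.02 to 0.10; 80% power; two-sided z-test at 0.05.

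**1. The plan's own figure.** Detectable effect = (1.96 + 0.84) × √(2 × DE / 45), with DE = 1 + (22.5 − 1) × ICC.

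- ICC 0.02: DE = 1.43, detectable effect 0.71.
- ICC 0.10: DE = 3.15, detectable effect 1.05.

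The plan states 0.6 to above 1.0. The upper end reproduces. The lower end does not: power at 0.6 is 66%. It is approached (0.61) only with an unstated baseline correlation of about 0.5.

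**2. How much of the noise is patient-level.** Arm-effect variance = ICC + (1 − ICC) × 2/45.

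- ICC 0.02: 0.0200 + 0.0436 = 0.0636; patient share 69%.
- ICC 0.10: 0.100 + 0.040 = 0.140; patient share 29%.

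**3. Precision from the second score (assumed correlations).** In simulation with entry decided by a cut-off on the entry score, retest correlation 0.6–0.8 and 10–30% screening positive, adding the entry score cut patient-level residual variance by about 4–13%.

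- ICC 0.02: 0.69 × 4–13% = 2.8–9.0% of arm-effect variance. Taking 1 − √(1 − cut), this is 1.4–4.6% of the detectable effect.
- ICC 0.10: 0.29 × 4–13% = 1.2–3.8% of the variance, or 0.6–1.9% of the detectable effect.

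These are slightly generous, because the first baseline already shrinks the patient share. A closed form agrees: with residual variance 1 − ρ² for one score and 1 − 2ρ²/(1 + ρ) for two, ignoring truncation, ρ = 0.5 gives 0.643 → 0.620 (3.5%) at ICC 0.02 and 1.010 → 0.997 (1.3%) at ICC 0.10. Over ρ 0.3–0.8 the gain is 1.8–4.6% and 0.7–1.4%. It would be 2.7–10.4% only if the second score also explained variance between clinics.

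**4. Precision from age and gender.** With an assumed partial R² of 0.02–0.10, the detectable effect falls by 0.6–3.2% at ICC 0.02 and 0.2–1.2% at ICC 0.10.

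**5. Bias when treatment does nothing.** Entry score S, initiation score B and outcome Y were simulated as equally reliable measures of one stable level. Entry required S at least 1 SD above the IPT-A source mean, and the TAU source was more severe by the gap shown. Entries are the false IPT-A benefit in SD.

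| Reliability | Gap | S only | B only | S and B | Removed (B → S and B) |
|---|---|---|---|---|---|
| 0.6 | 0.5 | 0.199 | 0.148 | 0.124 | 16% |
| 0.7 | 0.5 | 0.150 | 0.111 | 0.089 | 20% |
| 0.8 | 0.5 | 0.099 | 0.075 | 0.055 | 27% |
| 0.6 | 1.0 | 0.400 | 0.300 | 0.250 | 17% |
| 0.7 | 1.0 | 0.300 | 0.222 | 0.176 | 21% |
| 0.8 | 1.0 | 0.201 | 0.150 | 0.111 | 26% |

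Two columns can be checked by hand. With reliability r, S alone leaves gap × (1 − r): 0.5 × 0.4 = 0.20. S and B together leave gap × (1 − r)/(1 + r): 0.5 × 0.4/1.6 = 0.125.

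Varying the share positive over 10–30%, B alone leaves 0.07–0.32 SD and S with B leaves 0.055–0.25 SD, so about 14–32% is removed. With no gap, every model gives zero to within 0.003 SD.

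**The case against.** **Age and gender are already planned.** This stands. A reader might infer that they are left out of the analysis; they are only deferred. The gap is that neither model is named as the main one.

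**Selection on the entry score.** A reader might infer that, because that score decides entry and may be missing from the model, the arm effect is biased by regression to the mean, and that adding it cures this. The documents support neither. With equal source populations there is no arm bias under any of the models. With a gap, 68–86% of the bias survives the fix, because its source is the difference in recruitment. The documents report no severity gap. Under the same assumptions, unadjusted change from the initiation score shows no bias to within 0.002 SD, so what remains is the cost of covariate adjustment with error-prone scores across unlike populations.

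**The entry score may bring its own bias.** Providers take it in IPT-A and research assistants in TAU. If providers scored 0.2 SD higher on that score alone, then with no gap the bias would rise from about 0.04–0.05 to 0.07–0.09 SD. With a 0.5 SD gap there would be no gain (0.20 against 0.20 at retest 0.6; 0.16 against 0.17 at 0.7). This stands in part. Within each arm the same type of staff also takes the later scores, so a shift common to all scores is at least as natural, and under it adding the entry score reduced bias in every case with a gap or a shift. But the screening providers need not be the two trained group facilitators, so a shift confined to the entry score cannot be excluded.

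**The effect is small beside the noise.** This also stands. The standard errors are √0.0636 = 0.25 and √0.140 = 0.37 SD. Using a z-test with four clinics is a separate and much larger matter: on 2 degrees of freedom the detectable effect is about 1.4–2.1.

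**Conclusion.** The point holds as a modest improvement, not as a flaw that invalidates the comparison. Two things are certain from the text: baseline is undefined although two pre-treatment PHQ-A scores exist, and no main model is named. The sizes are conditional. The documents give no retest correlation, PHQ-A cut-off, positive rate, severity gap or R², so every gain and bias figure rests on the assumed ranges shown above. On those ranges the precision forgone is minor and the bias is only partly reducible. The clearest benefit is ruling out the entry score as sole baseline: for the same gaps it leaves 0.10–0.40 SD, against 0.07–0.32 SD for the initiation score.

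**What to change.** In Statistical Procedures, Quantitative analysis:

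- Define baseline as the treatment-initiation PHQ-A, including the first-scheduled-session rule for adolescents who do not start treatment.
- Name one main symptom model: arm, treatment-initiation PHQ-A, entry PHQ-A, age and gender as fixed effects, with PCC as random effect.
- Report the same model without the entry score as a sensitivity analysis. If the two arm estimates differ materially, say so and consider a scoring difference between providers and research assistants.
- State how a missing entry score is handled, so that nobody drops out of the intention-to-treat comparison.

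In Study procedures, for both arms, require the entry PHQ-A score to be copied into the study record at enrolment. In IPT-A this means taking it from the paper screening form.

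The cost is a few sentences and one already-measured number per adolescent, with no new visit or instrument. The change should be made before outcomes are examined by arm. For anyone already enrolled, it depends on the screening form having been kept. It does not repair the difference in recruitment between the arms, which should be stated as a limitation.
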